8.3 Analysis populations

The datasets derived from individual study subjects will be classified into following 3 classes prior to database lock and before carrying out any statistical analyses:

- Modified intention-to-treat (mITT) population: all randomised subjects who have received at least 1 dose of study treatment.
- Per-protocol (PP) population: Subjects who have completed the study according to the protocol without major protocol deviations.
- Safety population is the same as the mITT population.

8.4 Statistical analyses

Statistical analyses are described in more detail in the statistical analysis plan.

8.4.1 Demographic and other baseline characteristics

All relevant demographic and baseline characteristics will be summarised using descriptive statistics. The number and reasons for discontinuations will be listed and tabulated by treatment groups.

8.4.2 Treatment compliance and extent of exposure

The number of exposed subjects, the number of administered study treatments and the duration of study treatment exposure will be tabulated with descriptive statistics.

8.4.3 Pharmacokinetic analysis

The primary variable for the evaluation of PK of levodopa is AUC_{0-24} to describe the total levodopa exposure. The secondary PK variable is $C_{min,tau}$, which is used to describe minimum concentration during the dosing intervals. The ratio of the C_{max} in a dosing interval and the observed concentration at the end of the dosing interval, $C_{max}/C_{min,tau}$, which is used to describe levodopa fluctuation during the dosing intervals and other PK variables of levodopa, 3-OMD, carbidopa and ODM-104 will be evaluated as other variables.

PK parameters will be analysed after logarithmic transformation and 90% confidence intervals (CIs) for the geometric means will be calculated.

The conclusions regarding possible differences between different study treatments will be based on both overall evaluation of levodopa concentration-time profiles and formal statistical analyses of PK parameters.

Primary pharmacokinetic evaluation

The primary PK variable will be summarised using descriptive statistics by treatment and analysed using a mixed linear model with 90% CI applicable for the crossover design. The statistical model will include treatment and period as fixed effects and subject as random effect. Sensitivity analysis adjusted for subject weight and age will be performed.

Levodopa fluctuation ratios ($C_{\max}/C_{\min,\tau}$, $C_{\max}/C_{(16\text{ h})}$, PTF_{τ} and PTF_{0-16}), and AUC_{0-24} , C_{\max} and $C_{\min,\tau}$ will be the main PK variables of interest.

The primary conclusions will be based on the PP population.

Secondary pharmacokinetic evaluation

Statistical evaluation for secondary PK variable will be done using similar methods as for primary variable. Statistical model for $C_{\min,\tau}$ will include treatment, period, dosing interval, and treatment by dosing interval interaction as fixed effect and subject by period interaction as random effect.

Other pharmacokinetic evaluations

The other PK variables for the evaluation of PK of levodopa, carbidopa, 3-OMD and ODM-104 are presented in [Table 4](#). All PK variables will be summarised by treatment using descriptive statistics. Selected PK variables will be analysed using similar models and sensitivity analysis to the primary and secondary PK variables. Drug concentrations will be tabulated by time and treatment with descriptive statistics.

8.4.4 Pharmacogenomic analysis

In the context of this study, genetic polymorphisms may be analysed in relation to significant variation or specific scientific questions in PK or safety variables of levodopa, carbidopa or ODM-104. If such analysis is decided to be performed, a substudy will be designed and the results will be reported in a separate report.

8.4.5 Safety analysis

An authorised person will code AEs, medical history and concomitant diseases using standard coding dictionaries.

8.4.5.1 Analysis of adverse events

AEs will be classified by system organ classes and preferred terms using the Medical Dictionary for Regulatory Activities (MedDRA). The number and proportion of subjects reporting each AE and the number of events will be presented in a frequency table. The following AE data will be summarised: overview of AEs, severity of AEs and causality to the study treatment. SAEs, AEs leading to premature discontinuation of study treatment and other significant AEs will be evaluated case by case.

AEs occurring before and after the initiation of study treatment will be reported separately.

8.4.5.2 Clinical safety analysis

Vital signs (systolic and diastolic BP and HR) at each visit and change from baseline (screening value) in each vital sign will be summarised using descriptive statistics. 12-lead ECG parameters at each time point and change from baseline (screening value) will be summarised using descriptive statistics. Physical examination and C-SSRS findings will be tabulated.

8.4.5.3 Laboratory safety analysis

Laboratory values and changes from baseline (screening value) in laboratory values will be summarised using descriptive statistics. The number and proportion of subjects with laboratory values outside the normal range will be summarised by visit for each laboratory analyte.

8.4.5.4 Analysis of prior and concomitant treatments

Prior and concomitant treatments will be coded using the anatomical therapeutic chemical (ATC) classification system. The number and percentage of subjects using concomitant treatments will be summarised by a pharmacological subgroup and chemical substance.

8.5 Interim analyses

No interim analysis is planned for this study.

9. DATA QUALITY ASSURANCE

9.1 Training

An initiation meeting will be arranged for the investigators and other relevant study centre personnel. This meeting will include a review of the protocol, eCRF completion and study procedures.

The investigators will ensure that appropriate training relevant to the study is given to the medical, nursing and other personnel involved in the study. The investigators will also ensure that any information relevant to the conduct of the study is forwarded to other relevant study centre personnel.

9.2 Case report forms

Electronic queries about missing, misleading, incomplete or illogical data will appear in the EDC system. An audit trail within the system will track all changes/corrections made. The investigator has to confirm the content of the eCRF with an electronic signature.

9.3 Monitoring, audits and inspections

The study monitor will visit the study centre regularly as agreed by the investigator and the sponsor. The study monitor will ensure that the study complies with good clinical practice (GCP) and applicable regulatory requirements and that the protocol is followed in all aspects, including the randomisation procedure, accurate recording of results, reporting of AEs, drug accountability and record keeping. Furthermore, it will be verified that the clinical facilities remain appropriate, and that the eCRFs correspond with source data. Further details regarding monitoring are presented in the monitoring manual.

The study may be audited by independent representative(s) of the sponsor or inspected by the CAs. For these purposes, the study monitor, auditors and inspectors will be allowed direct access to source data of the study subjects, original laboratory data etc., as far as they are related to the study.

It is essential that the investigator and other relevant members of the study centre team are available during the monitoring visits, audits and inspections, and that they devote sufficient time to these processes.

9.4 Laboratories and other vendors

All blood and urine samples will be worked up and analysed in the CRO's clinical laboratory. ECGs will be recorded and analysed in the clinic of the CRO.

Details regarding laboratory safety assessments and ECG analyses are presented in separate instructions. Quality certificates are required from all safety laboratories.

Bioanalytics will be performed using validated methods.

10. FURTHER REQUIREMENTS AND GENERAL INFORMATION

10.1 Investigators and study administrative structure

10.1.1 Investigators

Should the principal investigator transfer one of his/her responsibilities to other members of the study centre team, he/she must have this documented.

In the event of changes in key study centre team members, the responsible investigator must ensure that the successor is fully informed and capable of following the procedures.

A curriculum vitae in English must be obtained from all investigators who sign the protocol, and from other relevant persons.

10.1.2 Data and safety monitoring board

No data and safety monitoring board will be established for this study.

10.2 Insurance

The sponsor will provide clinical trial liability insurance for study subjects according to local regulations.

10.3 Retention of records

The investigator agrees to keep the following documentation in the investigator's study file: study subject records, including a subject screening log, a subject identification list, all original signed IC forms, a copy of eCRFs and records of drug dispensing.

The study files will be stored in the respective archives for 15 years, after which the sponsor will be contacted and the possibility of future archiving will be mutually agreed upon.

10.4 Completion of the study

The study is estimated to start in February 2017 (first subject first visit) and end when the last subject's last visit takes place.

Upon completion of the study, all unresolved issues will be clarified and remaining study treatments and other study materials will be collected.

The sponsor reserves the right to prematurely terminate the study for valid scientific or administrative reasons. After such a decision, the investigator must contact all participating study subjects within 7 days, and invite them for an end-of-study visit. All eCRFs must be completed up to the end-of-study visit.

10.5 Reports, publications and communication of results

Orion wishes to collaborate with the investigator to publish the results as timely as possible, without compromising accuracy or industrial property rights. The preparation, submission and authorship for publications containing the study results shall be in accordance with a process determined by mutual written agreement among the sponsor and participating institutions, and in accordance with international criteria for authorship; see International Committee of Medical Journal Editors recommendations, available at <http://www.icmje.org>.

Orion remains the exclusive owner of the study data defined by the protocol.

This study will be registered in one of the acceptable registries before the enrolment of the first subject.

11. ETHICS

11.1 Ethics committee

The study protocol, subject information sheet, IC form, and all other necessary documents will be submitted to an independent EC for review according to local regulations.

A favourable opinion will be obtained from the EC for the study, as well as any amendment(s), and communication of study-related safety issues as requested by the EC. The investigator should file all correspondence with the EC in the investigator's study file. Relevant copies of this correspondence should be forwarded to the sponsor.

11.2 Ethical conduct of the study

The study will be conducted in accordance with the Declaration of Helsinki guiding physicians in biomedical research involving human subjects.

The study shall not be initiated before favourable opinion from the EC and approval from the CA has been obtained for the protocol.

The study will be conducted in compliance with the protocol, GCP (ICH/135/95) and applicable regulatory requirements. A substantial amendment shall not be implemented until the protocol amendment has received a favourable opinion from the EC and approval from the CA. Only in case of the need to eliminate an immediate hazard(s) to study subjects, the investigator may implement deviation from the protocol without prior favourable opinion from the EC and approval from the CA for the protocol amendment.

11.3 Subject information and informed consent

The investigator will ensure that each subject is fully informed about the objectives and procedures of the study. The investigator will also explain any possible risks with participating in the study and answer all questions regarding the study. The subject will be given sufficient time to make a decision regarding participation in the study.

Subjects will be informed of their right to discontinue the study at any time without their medical care or legal rights being affected. Subjects will also be informed that representatives of the sponsor or CA may inspect relevant parts of their medical records and study data.

The investigator will obtain a signed and dated consent from each subject before any study related procedures are performed. One original of the signed and dated IC will be given to the subject. A second original will be retained in the investigator's study file. The investigator should confirm the receipt of every IC by entering the date of the consent both on the subject's eCRF and also on the subject screening log and identification list.

11.4 Subject data protection

Information collected during the course of the study will be stored in a database and used in the further development of study treatments and thereafter for as long as the information is relevant to patient care. The use includes the transfer of data to CAs in the European Union, the United States or other countries for the purpose of obtaining and maintaining marketing authorisations. All information is handled confidentially and according to local laws and regulations.

The study subjects can be identified in the eCRFs only by study subject number, sex, year of birth, age and racial group.

The confidentiality of PG data will be protected according to local laws and regulations.

## 1 Abbreviations

|                  |  |
|------------------|--|
| AE               | Adverse event                              |
| AUC              | Area under the concentration-time curve    |
| BMI              | Body mass index                            |
| BP               | Blood pressure                             |
| C max | Peak concentration in plasma               |
| C min | Minimum observed concentration             |
| CV               | Coefficient of variation                   |
| ECG              | Electrocardiogram                          |
| HR               | Heart rate                                 |
| IR               | Immediate release                          |
| ITT              | Intention-to-treat                         |
| MR               | Modified release                           |
| PD               | Parkinson's disease                        |
| PG               | Pharmacogenomic(s)                         |
| PK               | Pharmacokinetic(s)                         |
| PP               | Per-protocol                               |
| SAE              | Serious adverse event                      |
| t ½   | Terminal elimination half-life             |
| t max | Time to reach peak concentration in plasma |

## 2 General remarks

The purpose of this document is to describe the statistical methodology for this clinical study, including also plans of populations to be used and the plans how the results will be presented.

## 3 Overall study design and plan

This is a phase I, open, repeated dose, randomised PK study in healthy males. The study will be conducted at one centre.

The study will consist of 4 parallel groups (Groups 1-4). All groups will have a crossover design with 4 treatment periods, each lasting for 7 days. The total duration of the study will be approximately 10-15 weeks for each study subject.

## 4 Study objectives

### 4.1 Primary objective

The primary objective is to compare PK of levodopa after repeated administration as follows (Groups 1-4):

Group 1:

- A1=50 mg of MR levodopa + 12.5 mg of carbidopa
- B1=50 mg of MR levodopa + 65 mg of carbidopa
- C1=50 mg of MR levodopa + 65 mg of carbidopa + 50 mg of ODM-104
- D1=50 mg of MR levodopa + 65 mg of carbidopa + 100 mg of ODM-104

Group 2:

- A2=100 mg of MR levodopa + 25 mg of carbidopa
- B2=100 mg of MR levodopa + 65 mg of carbidopa
- C2=100 mg of MR levodopa + 65 mg of carbidopa + 50 mg of ODM-104
- D2=100 mg of MR levodopa + 65 mg of carbidopa + 100 mg of ODM-104

Group 3:

- A3=150 mg of MR levodopa + 37.5 mg of carbidopa
- B3=150 mg of MR levodopa + 65 mg of carbidopa
- C3=150 mg of MR levodopa + 65 mg of carbidopa + 50 mg of ODM-104
- D3=150 mg of MR levodopa + 65 mg of carbidopa + 100 mg of ODM-104

Group 4:

- A4=100 mg of IR levodopa + 25 mg of carbidopa (Sinemet®)
- B4=100 mg of MR levodopa + 65 mg of carbidopa
- C4=100 mg of MR levodopa + 25 mg of carbidopa + 100 mg of ODM-104
- D4=100 mg of MR levodopa + 65 mg of carbidopa + 100 mg of ODM-104

The primary objective is to compare PK of 3 different strengths of levodopa after repeated administration in combination with carbidopa and ODM-104.

ODM-104 and carbidopa dose effects will be studied with the 3 MR levodopa strengths and compared with the standard levodopa formulation. Primary comparisons for each of the 4 treatment groups will be performed for levodopa PK between the treatments. The resulting PK data will be used to select the optimal combination of levodopa, carbidopa and ODM-104 for subsequent clinical studies.

### 4.2 Secondary objectives

The secondary objectives are to determine the PK properties of 3-OMD, carbidopa and ODM-104 in plasma after repeated administration of the different combinations.

## 5 Statistical hypotheses

The primary variable for the evaluation of PK of levodopa is  $AUC_{0-24}$  to describe the total levodopa exposure. Primary comparison will be made within levodopa dose level groups, between crossover treatment arms levodopa / 12.5, 25 or 37.5 mg of carbidopa and levodopa / 65 mg of carbidopa / 100 mg of ODM-104. I.e. comparisons A1 vs. D1, A2 vs. D2, A3 vs. D3, and A4 vs. D4 will be the primary ones.

Other crossover comparisons will be performed and considered as secondary. Parallel group comparisons may be performed. The conclusions on possible differences between treatments will be based on both overall evaluation of levodopa concentration-time profiles and formal statistical analyses of PK parameters.

$H_0: AUC_{0-24, \text{levodopa/carbidopa / ODM-104}} = AUC_{0-24, \text{levodopa/carbidopa}}$

$H_1: AUC_{0-24, \text{levodopa/carbidopa / ODM-104}} \neq AUC_{0-24, \text{levodopa/carbidopa}}$

## 6 Determination of sample size

The sample size estimation is based on earlier ODM-104 phase I study 3112003. Sample size is estimated using the  $AUC_{0-24}$ . Sample size estimation is based on the results from 12 subjects that completed treatment periods with levodopa 100 mg / carbidopa 25 mg / entacapone 200 mg and MR levodopa 100 mg / carbidopa 65 mg / ODM-104 100 mg. The latter treatment arm with ODM-104 and 65 mg of carbidopa increased exposure by 22% ( $AUC_{0-24}$  14022.2 vs. 17092.6). Within subject variability is estimated to be 0.1386 ( $\sqrt{MSE}$  in logarithmic scale). It is assumed that MR levodopa 100 mg / carbidopa 65 mg / ODM-104 100 mg will increase exposure by 40% compared to MR levodopa 100 mg / carbidopa 25 mg.

When the sample size in each sequence is 3 (with a total sample size of 12), a crossover design will have 80% power to detect a difference in means of 0.336 assuming that the within subject variation is 0.139 using a crossover ANOVA with a 0.1 two-sided significance level. To allow drop outs 14 subjects per group and 56 subjects in total will be randomized into this study with 4-treatment, 4-period William's crossover design. This will provide adequate power for the primary comparison. In case there are premature discontinuations the sponsor will decide case-by-case whether replacement subjects will be entered into the study. Replacement subjects will be randomized to go through all 4 treatment periods. Discontinued study subjects are not allowed to re-enter the study.

## 7 General statistical considerations

### 7.1 Analysis populations

The datasets derived from individual study subjects will be classified into following three classes prior to database lock and before carrying out any statistical analyses:

- Modified intention-to-treat (mITT) population: all randomized subjects who have received at least one dose of study treatment. The difference between ITT and mITT is that subjects in mITT will be included to have the treatment actually administered. In ITT, subjects are included in the treatment they were intended to be administered.

- Per-protocol (PP) population: Subjects who have completed the study according to the protocol without major protocol violations.
- Dosing intervals, where subject experience emesis during the treatment period at Day 7 and following dosing intervals during the period, will be removed from analysis using PP population.
- Periods with PK parameters covering entire Day 7 (e.g.  $AUC_{\infty}$ ) will be excluded from the PP population analysis entirely, in case of emesis.
- If the emesis is experienced at time point 14 hours or thereafter during the last dosing interval, the dosing interval and period will be included into the PP population
- Safety population is the same as the modified ITT population.

The role of each population is described in Table 1.

Table 1. Populations that will be used in tabulations and statistical analyses.

| Primary efficacy variable | Secondary efficacy variables | Demographics
Additional variables | Safety variables  |
|---------------------------|------------------------------|--------------------------------------|-------------------|
| PP                        | PP                           | mITT                                 | Safety population |
| mITT                      | mITT                         |                                      |                   |

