### 7.2.2 Handling of dropouts or missing data

In general, missing data or partial data will not be imputed, and statistical analyses will be performed for observed cases only. Possible missing data will be included in statistical calculations via mixed models theory, where missing data can be utilized by setting the subject as random effect in the statistical model. Possible sensitivity analyses may be carried out to evaluate the robustness of the statistical results, that is, particularly the impact of potential outliers.

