## 8 Statistical analyses to be used in this study

### 8.1 Disposition of subjects

The number of subjects will be tabulated for the following populations:

- Screened
- Randomised
- Modified ITT
- PP
- Safety
- Discontinued study
- Completed study

The disposition and number and reasons for withdrawal and discontinuations will be listed and, if needed, tabulated by treatment sequence. Reasons for excluding subjects or subject periods from pharmacokinetic analyses will be listed. Data from subjects who failed at screening will be included only in the disposition tabulations and data listings.

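### The per-protocol set behind the primary conclusions admits only study completers, so a dropout's valid periods are left out of it; the cost is modest and a subject-period definition would remove it

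*SAP*

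**What the plan says.** Both documents make PP membership a property of the subject and tie it to finishing the study. SAP 7.1 has "Subjects who have completed the study according to the protocol without major protocol violations", and protocol 8.3 has the same rule: "Subjects who have completed the study according to the protocol without major protocol deviations". Protocol 8.4.3 states: "The primary conclusions will be based on the PP population".

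Other parts of the SAP work at a finer level:

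- **Emesis (SAP 7.1).** For dosing-interval parameters, the affected and following intervals of that day 7 are dropped. For parameters spanning all of day 7, such as AUC0-24, the period "will be excluded from the PP population analysis entirely, in case of emesis". Emesis at 14 h or later excludes nothing.
- **Disposition (SAP 8.1).** "Reasons for excluding subjects or subject periods from pharmacokinetic analyses will be listed".
- **Dropouts and missing data (SAP 7.2.2).** "Possible missing data will be included in statistical calculations via mixed models theory", on the ground that "missing data can be utilized by setting the subject as random effect in the statistical model". This is not limited to one population.
- **Model (SAP 8.4.1).** Treatment and period are fixed and subject is random, so incomplete subjects can be used.

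SAP Table 1 assigns both PP and mITT to the primary and secondary variables. The mITT set is "all randomized subjects who have received at least one dose of study treatment".

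**The concern.** Two subjects with equally good data are treated differently. One completes the study but vomits in one period before 14 h: the other three AUC0-24 values stay in PP. The other has three clean periods and then leaves: all three values go. The model does not require this, and neither document gives a reason.

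Within PP, the SAP 7.2.2 provision can therefore act only on completers' missing or emesis-removed periods. It cannot act on dropouts, because PP contains none.

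Two things are at stake. The first is precision. The second is selection: protocol 4.5 lists intolerable dopaminergic and gastrointestinal events among the reasons for discontinuing, and these could be related to levodopa exposure, which is the primary variable. The results are meant to guide the choice of combination (protocol 2.1), so an avoidable restriction to completers is worth removing.

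**Working it through.** **1. Which periods each planned set keeps (AUC0-24)**

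| Period | PP | mITT |
|---|---|---|
| Clean period of a completer with no major deviation | kept | kept |
| Clean period of a subject who later drops out | excluded | kept |
| Period with emesis before 14 h | excluded | kept (no emesis rule is written for mITT) |
| Period with a major deviation | excluded, with the whole subject | kept |

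No column contains every evaluable period and nothing else.

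**2. The plan's own power figure**

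Inputs from protocol 8.2 and SAP 6: 12 subjects, log difference 0.336 (ln 1.40 = 0.3365), within-subject SD 0.139, two-sided alpha 0.10.

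- SE = 0.139 × √(2/12) = 0.0567.
- Noncentrality = 0.336 / 0.0567 = 5.92, with 3 × 11 − 3 = 30 df.
- Power = 0.99998.

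The stated 80% is therefore not reproduced and is true only as a lower bound. That is a separate matter, and the point here does not depend on it.

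**3. Number of dropouts**

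No rate is given. Randomising 14 to secure 12 implies 2 per group (2/14 = 14.3%).

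**4. Precision of completers-only against all observed periods**

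Design: 14 subjects on the four Group 1 example sequences in protocol Table 2 (4, 4, 3 and 3 subjects), treatment and period fixed, subject random. The variance of A−D is the matching diagonal element of (XᵀV⁻¹X)⁻¹. Here V has 0.139² for within-subject variance, plus a between-subject variance shared by all periods of a subject.

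Assumptions not in the documents: between-subject log SD 0.15–0.35, and the timing of dropout. Dropouts are drawn at random and results averaged over several hundred patterns. With no dropouts the SE is 0.0527.

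| Dropouts of 14 | When they leave | SE, all periods | SE, completers only | Increase in SE |
|---|---|---|---|---|
| 2 | after period 1 | 0.0567–0.0571 | 0.0573 | about 0.3–1% |
| 2 | after period 1, 2 or 3, equally likely | 0.0554–0.0556 | 0.0573 | about 3% |
| 2 | after period 3 | 0.0540–0.0542 | 0.0573 | about 6% |
| 4 | after period 1 | 0.0618–0.0628 | 0.0633 | about 1–2.5% |
| 4 | equally likely | 0.0585–0.0591 | 0.0634 | about 7–8% |
| 4 | after period 3 | 0.0555–0.0557 | 0.0633 | about 14% |

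The valid periods set aside with 2 dropouts number 2, 4 (on average) and 6 in the three timings.

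**5. What this means for the result**

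- *Interval width.* Take 2 dropouts after period 3, using t(0.95, 30 df) = 1.697 for both sets. The 90% limits lie a factor exp(1.697 × 0.0541) = 1.096 from the estimated ratio with all periods, and exp(1.697 × 0.0573) = 1.102 with completers only.
- *Power for 0.336.* With 4 dropouts, completers-only gives noncentrality 0.336 / 0.0633 = 5.31 on 24 df, and power 0.9998.
- *Power for a smaller effect.* At the 22% increase seen in the earlier study (ln 1.22), with 2 dropouts and even timing, power is 96.0% for completers only and about 96.8% with all periods.

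**The case against.** The strongest reply is that this is a choice of primary set. SAP 7.2.2 is a general rule and can operate fully in the planned mITT analysis, where dropouts' periods are used. In PP it still handles completers' gaps. A reader might infer that the completers-only definition contradicts 7.2.2, or that dropouts' data are lost to the study. The documents support neither: the provisions can coexist, and SAP Table 1 plans the mITT analysis of AUC0-24. That part of the reply stands.

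The sample size also anticipates losses. Each group is sized on 12, 14 are randomised, and the sponsor may replace dropouts case by case. A PP set of 12 is the planned situation, so the 4-dropout rows go beyond the implied allowance and assume no replacement. This stands too.

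It can be added that agreement between PP and mITT would largely settle the matter. It would reassure, but the sets differ in dropouts, emesis and major deviations together. If they disagreed, the comparison could not show which caused it, and the documents do not say how a disagreement would be read beyond giving PP precedence.

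On selection, it is tempting to say that PP represents only men who tolerated all four treatments, or that the primary estimate is biased. That goes too far. A completer who vomits stays in PP with the affected data removed. Protocol 4.5 also lists discontinuation for personal reasons, loss to follow-up and protocol deviations, and the contrast is within subject. What remains is a possibility of selection, with no direction or size established.

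**Conclusion.** The point holds as a modest weakness in the definition of the primary analysis set. Read literally, PP drops every valid period of a subject who does not complete, while the SAP's emesis rules drop only the affected data, and no planned set contains exactly the evaluable periods.

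The loss depends mainly on when subjects leave and hardly on the assumed between-subject SD, except for the small figures after period 1. At the implied two dropouts per group, the SE rises by between a fraction of 1% and about 6%. Larger losses need more dropouts than planned and no replacement. The conclusion on the assumed 40% effect would not change for lack of power. The case for changing the definition is that it is inexpensive, recovers data already collected and removes an avoidable selection on completion. No error in the expected result has been demonstrated.

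**What to change.** Define PP by subject-period: include every period in which the treatment was taken as planned, day 7 pharmacokinetics are evaluable, and no major deviation or emesis (under the existing SAP rules) affects that period, whether or not the subject later completes the study. Classify periods before database lock, as already planned for subjects.

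Make the change in both protocol 8.3 and SAP 7.1, or record it in SAP 8.7 as a departure from the protocol. Changing SAP 7.1 alone without that record would leave the two documents disagreeing. The SAP 8.4.1 model code can stay as it is, and no further data or subjects are needed.

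The cost is a documented change to the protocol definition and slightly unequal numbers of subjects per treatment.
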